6.11 Follow up visit 8 (18 month \pm 7 days)

- Review medical and dental history, and concomitant medications
- Record blood pressure and pulse
- Oral examination
- Record adverse events as reported by participant or observed by investigator (Research purposes)
- Standardized peri-apical radiographs, if needed
- Oral photographs

6.12 Final study visit 9 (24 month \pm 7 days) End of study assessments

- Review medical and dental history, and concomitant medications
- Record blood pressure and pulse
- Oral examination
- Record adverse events as reported by participant or observed by investigator (Research purposes)
- Provide any final instructions to participant
- Standardized peri-apical radiographs, if needed
- Oral photographs

6.13 Unscheduled and/or Early Termination visits

If necessary one or more visits will be performed at any time for post-operative care.

- Review medical and dental history, and concomitant medications
- Oral examination
- Record adverse events as reported by participant or observed by investigator (Research purposes)
- Standardized peri-apical radiographs, if necessary
- Oral photographs, if necessary

CONFIDENTIAL

This material is the property of the NYU College of Dentistry. Do not disclose or use except as authorized in writing by the study sponsor

7 Statistical Plan

7.1 Sample Size Determination

Two test site bone samples will be compared with regard to microscopic measures of percent vital bone and residual graft material. The average of three histological specimens for each test sites of the subject biopsy will be calculated. Mean percent vital bone and percent residual graft material and standard deviations for each condition will be calculated. Condition comparisons will be made by two sided paired t-test. Sample size assumptions: Froum (2006) showed Puros M(SD) vital% of 28.2(14.0) and residual% of 7.7(9.2). Given 10 subjects in a repeated measures design, a paired t-test has power of 80% to detect a 1 SD difference in vital%, i.e., a 50% change from the level demonstrated by Froum et al. (2006). Nevins (2016) showed MinerOss vital% of 20.9 (5.0%), suggesting a necessary change of 25% for 80% power in a paired t-test at $p = .05$. The necessary change in residual% is higher, at least a 100% change from the Froum level. Thus, previous studies indicate that a 25-50% difference may be detected between conditions in vital % and a 100% difference in residual graft with a sample size of 10 subjects, 80% power, and 95% confidence.

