Statistical Methodology	Two test site bone biopsies will be compared with regard to microscopic measures of percent vital bone and residual graft material. The average of three histological specimens for each test sites of the subject biopsy will be calculated. Mean percent vital bone and percent residual graft material and standard deviations for each condition will be calculated. Condition comparisons will be made by two-sided paired t-test. Sample size assumptions: Previous studies indicate that a sample size of 10 subjects will have 80% power to detect a 25-50% difference in percent vital bone and 100% in residual graft material with 95% confidence.

CONFIDENTIAL

This material is the property of the NYU College of Dentistry. Do not disclose or use except as authorized in writing by the study sponsor

1 Introduction

This document is a protocol for a human research study. This study is to be conducted in accordance with US government research regulations, and applicable international standards of Good Clinical Practice, and institutional research policies and procedures.

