The sinus augmentation procedure was developed by clinicians in order to increase the amount of bone for the placement of dental implants. The sinus augmentation, or 'sinus lift' is a chairside dental surgery procedure, whereby a window is surgically created in the upper jaw near the sinus, the delicate sinus membrane is elevated, and bone substitute material is placed into the sinus. The gingiva and oral mucosa are then sutured and the sinus is allowed to heal for a period of about six months. The bone substitute material that is used in the sinus augmentation has varied considerably, and while many different bone substitute materials perform adequately, the ideal bone substitute composition has to date not been defined. Previous studies have examined the amount of new bone formation, and the amount of residual graft material from core biopsies taken after the sinus augmentation period were examined histologically (under the microscope). Classical studies have shown that normal human maxillary jaw bone is comprised of approximately 40% bone and 60% other tissues. To date the best results obtained by using human donor bone allograft, have resulted in 25% bone formation and 75% other tissues. The size and source of the allograft materials has been controversial. Cortical bone is the thicker denser outer bone, such as is found at the surface of the jaw, while cancellous bone is the more porous, spongier bone found within the jaw. The particle size of these two bone graft types is also important, particle size is important for the attraction of new bone cells into the graft, but also to provide a scaffold for the maintenance of volume of the bone graft. Clinicians have traditionally chosen larger bone graft particle size in the belief that they provide a more durable scaffold thus ensuring maintenance of the bone graft volume. It has previously been demonstrated that the large particle sizes perform adequately, for dental implants, but our early results suggest that by adding smaller particle sizes to the bone graft mix, a higher proportion of new bone may be obtained without loss of graft volume. The ultimate goal would be to define the type and particle size that is optimal for new bone formation that is the same or greater density as native bone.

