1.2 STUDY DEVICE

Bone graft material will consist of four to six grams of commercially available human donor bone allograft (Puros Allograft Bone Particles, Zimmer Biomet, Warsaw, IN USA) consisting of cortical and cancellous

CONFIDENTIAL

This material is the property of the NYU College of Dentistry. Do not disclose or use except as authorized in writing by the study sponsor

bone chips of both 250-1000 microns, and 1000-2000 microns size, or 1000-2000 microns size alone. The method and composition of these products has been described, both products are FDA approved and commercially available. The harvesting and processing of the graft materials is briefly described as follows:

Puros Allograft Bone Particles are sterile, dehydrated cortical and/or bone from donated human tissue with the Tutoplast® Process. The donated human tissue utilized for this implant was recovered from a donor screened for risk factors associated with infectious diseases and medical conditions that rule out donation. The donor's blood was tested for relevant communicable diseases in a laboratory certified under the Clinical Laboratory Improvement Amendments of 1988 (CLIA) or equivalent and registered with the U.S. Food and Drug Administration (FDA) for donor testing. The following test criteria were met for this donor:

REQUIRED INFECTIOUS DISEASE TESTING BLOOD TEST ACCEPTABLE RESULT

- HIV-1 / HIV-2 Antibody Negative/ Non-Reactive
- Hepatitis C Virus Antibody Negative/ Non-Reactive
- Hepatitis B Surface Antigen Negative/ Non-Reactive
- Hepatitis B Core Antibody (Total) Negative/ Non-Reactive
- Syphilis Negative/ Non-Reactive
- Human T-Cell Lymphotropic Virus I/II Antibody Negative/ Non-Reactive
- HIV-1 NAT-TMA Negative/ Non-Reactive
- HCV NAT-TMA Negative/ Non-Reactive

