7.2 Statistical Methods

The primary outcomes for this study are percent vital bone, and residual graft material. Patient age, sex, and health status will be described. Two test site bone biopsies will be compared with regard to microscopic measures of percent vital bone and residual graft material. The average of three histological specimens for each test sites of the subject biopsy will be calculated. Mean percent vital bone and percent residual graft material and standard deviations for each condition will be calculated. Previous studies indicate that the primary outcome variable is normally distributed. Tests for normalcy will be done. In the event that the distributions are skewed, and appropriate non-parametric test will be used. Otherwise, comparisons of the two conditions will be made by two sided paired t-test. A p value less than 0.05 will be considered significant. Radiographic examinations will be quantified by measuring bone height at three sites at each sinus augmentation site and then averaged for analysis.

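### The stated 80% power for a 25-50% difference in percent vital bone merges two products; the Puros figures alone support only about a 50% (14-point) difference

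*Combined protocol and SAP*

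**What the plan says.** Section 7.1 fixes the sample at 10 subjects and works back to the difference that can be detected. It states: "Given 10 subjects in a repeated measures design, a paired t-test has power of 80% to detect a 1 SD difference in vital" bone, and equates 1 SD with a 50% change from a Puros mean of 28.2% (SD 14.0). It then brings in a second study, which "showed MinerOss vital% of 20.9 (5.0%), suggesting a necessary change of 25% for 80% power in a paired t-test". Its last sentence joins the two results: "Thus, previous studies indicate that a 25-50% difference may be detected between conditions in vital" bone percentage, at 80% power and 95% confidence.

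The Study Summary, under Statistical Methodology, gives only the joined result: "Previous studies indicate that a sample size of 10 subjects will have 80% power to detect a 25-50% difference in percent vital bone". It names no product and no SD.

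Section 1.2 describes the graft as "commercially available human donor bone allograft (Puros Allograft Bone Particles, Zimmer Biomet, Warsaw, IN USA"). Section 5.1 also names Puros, and no other allograft brand is planned for either side. The test is specified in 7.1 ("Condition comparisons will be made by two sided paired t-test") and the threshold in 7.2 ("A p value less than 0.05 will be considered significant").

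**The concern.** The two ends of the range are not two effect sizes for one product. They are the same effect, 1 SD, expressed as a percentage of two different means with two different SDs. For Puros the SD is about half the mean; for MinerOss it is about a quarter. Joined together, they read as though the trial had 80% power anywhere between 25% and 50%, which the Puros inputs do not support at the lower end.

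Percent vital bone is a primary outcome, and this calculation is the only justification given for 10 subjects. A reader of the Study Summary alone cannot see that the more favourable end comes from another product. That matters most if the result is not significant, because the stated power would make a 25% difference look much less likely to have been missed than it is. Section 7.2 plans means, SDs and a p value but no confidence interval for the difference, so nothing in the planned reporting would correct that impression.

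**Working it through.** **Inputs**
- 10 pairs; two-sided paired t-test (7.1); alpha 0.05 (7.2).
- Puros: mean 28.2, SD 14.0 (7.1). SD/mean = 14.0/28.2 = 49.6%.
- MinerOss: mean 20.9, SD 5.0 (7.1). SD/mean = 5.0/20.9 = 23.9%.
- Not given: the SD of the within-subject differences, or the left-right correlation.

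**Method.** With d = difference / SD of paired differences, power is P(|T| > 2.262), where T is noncentral t with 9 degrees of freedom and noncentrality d × √10.

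**Step 1: reproduce the plan's figure.** At d = 1, power is 80.3%. This matches the stated 80%, and it does so by taking the SD of paired differences to equal the quoted SD. A one-sided test would give 89.8% and a normal approximation 88.5%, so the two-sided paired t is evidently what was used. The d with exactly 80% power is 0.996.

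**Step 2: each end on its own source.**
- Puros: 0.996 × 14.0 = 13.9 points; 13.9/28.2 = 49%. A 50% change is 14.1 points, d = 14.1/14.0 = 1.007, power 80.9%.
- MinerOss: 0.996 × 5.0 = 4.98 points; 4.98/20.9 = 23.8%. A 25% change is 5.225 points, d = 5.225/5.0 = 1.045, power 83.6%.

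Both ends are correct for the study they come from.

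**Step 3: the 25% end on Puros inputs.** 0.25 × 28.2 = 7.05 points; d = 7.05/14.0 = 0.504; power 29.7%.

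**Step 4: dependence on the unstated correlation.** If both sites have SD 14.0, the SD of differences is 14.0 × √(2(1 − ρ)). The plan's convention corresponds to ρ = 0.5. The other values of ρ are assumptions.

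| ρ | SD of differences | Power, 25% change | Change with 80% power |
|---|---|---|---|
| 0 | 19.8 | 17% | 70% |
| 0.3 | 16.6 | 23% | 59% |
| 0.5 | 14.0 | 30% | 49% |
| 0.7 | 10.8 | 45% | 38% |
| 0.8 | 8.9 | 61% | 31% |
| 0.9 | 6.3 | 89% | 22% |

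For 80% power at a 25% change, the SD of differences must be 7.05/0.996 = 7.08, so ρ = 1 − (7.08/14.0)²/2 ≈ 0.87.

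**Step 5: what the interval would show.** At an SD of differences of 14.0, the 95% confidence interval half-width is 2.262 × 14.0/√10 = 10.0 points. An observed difference of zero would leave 7.05 points, the 25% change, well inside the interval.

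**The case against.** The best defence is that 7.1 hides nothing. It names both products, gives both means and SDs, attaches each percentage to its source, and says only that such a difference may be detected. Using two published SDs to bracket an uncertain one is ordinary planning. This stands to the extent that 7.1 contains no calculation error, and a careful reader can recover the Puros-only figure from it. It does not rescue the joined range, which is presented as a span of detectable differences rather than as uncertainty about the SD. Nor does it cover the Study Summary, which drops the sources and says that 10 subjects will have the power.

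A second defence is that sharing a brand name does not make 14.0 the right SD. The documents do not give the particle size, composition or healing time behind either cited figure; one arm is a four-part mixture and the other is large cancellous particles. This also stands. It argues for stating the assumption, not for taking another product's mean and SD without comment.

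Three stronger readings are tempting but unsupported:
- *That the trial's real power at 25% is 30%.* That figure is conditional on an SD of differences of 14.0, which the documents neither give nor rule out.
- *That the Puros target is implausible.* A 14-point gain takes 28.2% to 42.2%, while 1.1 says "normal human maxillary jaw bone is comprised of approximately 40% bone and 60% other tissues". But 1.1 also sets the ultimate goal at native density or greater, so the target may be ambitious without contradicting the protocol.
- *That the trial must be enlarged.* On the same convention, 33 pairs would be needed for 80% power at 25%, but the protocol nowhere names 25% as a difference that it must detect.

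**Conclusion.** The power statement is wrong as written for the product under study. On the only Puros figures in the documents, 10 pairs give 80% power for about 14 points (50%). The 25% end depends on the MinerOss mean and SD. Under the plan's own implied convention, power for a 25% change on the Puros inputs is about 30%; across assumed correlations from 0 to 0.9 it runs from 17% to 89%, passing 80% only near 0.87. The conclusion that 25% is unsupported on the Puros inputs therefore holds unless the two sides are very strongly correlated, and no such correlation is claimed.

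A reader might infer that the plan treats a non-significant result as excluding a 25% difference. No passage says so, and there is no equivalence or futility rule. The fault is in the stated power, most visibly in the Study Summary, and not in the choice of test, alpha or sample size.

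**What to change.** In the Study Summary and the last sentence of 7.1, replace the 25-50% range with wording such as:

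> 10 evaluable pairs give 80% power for a difference of 1 SD of the paired differences. If that SD is 14.0 (the cited Puros SD), this is about 14 points (50%), and power for a 25% difference is about 30%.

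Keep the 25% figure only as a sensitivity case, labelled as applying if variability matches the MinerOss study. In 7.1, state that the SD of paired differences is assumed equal to the quoted SD (correlation 0.5 if the site SDs are equal), and give the range: power for a 25% difference is 17% at correlation 0, 61% at 0.8, and 80% only near 0.87.

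In 7.2, add that the mean paired difference will be reported with its 95% confidence interval, with an expected half-width of about 10 points at SD 14. A non-significant result can then be read by what the interval excludes.

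The cost is text edits in the two places and one reporting line, plus a less favourable headline for sensitivity. No patients or visits are added, and the sample size, test and alpha stay as they are.

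### Residual graft: 80% power is claimed for a 100% change, but the protocol's own 1 SD rule and inputs give about 119%, and about 65% power at 100%

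*Combined protocol and SAP*

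**What the plan says.** Section 7.1 (Sample Size Determination) plans a two-sided paired t-test on 10 subjects, each contributing both conditions. It takes mean (SD) values from two earlier studies. The first, with Puros, gives vital bone 28.2 (14.0) and residual graft 7.7 (9.2). The second, with MinerOss, gives vital bone 20.9 (5.0).

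The working rule is "Given 10 subjects in a repeated measures design, a paired t-test has power of 80% to detect a 1 SD difference in vital" bone percentage, which the section equates to a 50% change using the first study. The second study's values are said to need a 25% change. For residual graft the section says: "The necessary change in residual% is higher, at least a 100% change" from the first study's level. Its closing sentence then claims "a 100% difference in residual graft with a sample size of 10 subjects, 80% power, and 95% confidence".

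The Study Summary, under Statistical Methodology, claims "80% power to detect a 25-50% difference in percent vital bone and 100% in residual graft material", with no qualifier.

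Section 7.2 (Statistical Methods) states: "The primary outcomes for this study are percent vital bone, and residual graft material". It sets significance at p below 0.05. No left-right correlation and no SD of the paired differences is given anywhere.

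**The concern.** The residual-graft SD is larger than its mean. A rule that turns 1 SD into a percentage of the mean must therefore give more than 100%. The sentence that says at least 100% is compatible with that. The closing sentence and the Study Summary turn this lower bound into a point value and attach 80% power to it.

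Residual graft is one of two primary outcomes. If the power for a 100% change is overstated, a null result could be read as reasonable evidence against a change of that size when the design would often miss it. The figure also depends on a correlation that the documents do not state.

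**Working it through.** **Inputs.** n = 10 pairs, two-sided paired t-test, alpha 0.05 (Sections 7.1 and 7.2). Vital bone 28.2 (14.0) and 20.9 (5.0); residual graft 7.7 (9.2) (Section 7.1). The left-right correlation ρ is not given and is varied below.

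**Formulas.** SD of the differences = SD × √(2(1 − ρ)). Standardised difference d = mean difference / SD of the differences. Power comes from the noncentral t distribution with 9 degrees of freedom and noncentrality d × √10.

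**Step 1: the plan's rule.** At d = 1, power is 80.3%. Exactly 80% power needs d = 0.996. The rule is correct when the SD is that of the paired differences.

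**Step 2: the implied correlation.** Section 7.1 puts in the one-condition SD. That equals the SD of the differences only when √(2(1 − ρ)) = 1, that is ρ = 0.5.

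**Step 3: the plan's vital-bone figures.**
- First study: 14.0/28.2 = 49.6% (stated 50%).
- Second study: 5.0/20.9 = 23.9% (stated 25%).

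Both reproduce. A 50% change (14.1 points, SD 14.0) has 80% power for ρ of about 0.49 or more. A 25% change (5.225 points, SD 5.0) has it for ρ of about 0.45 or more.

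**Step 4: the same rule for residual graft.** 9.2/7.7 = 119.5%. With the exact multiplier, 0.996 × 9.2 = 9.16 points, and 9.16/7.7 = 119.0%. The plan states 100%.

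**Step 5: power at the stated 100%.** d = 7.7/9.2 = 0.837, which gives power 65.5%. The chance of a miss is about 35%, against the 20% that 80% power implies.

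**Step 6: dependence on the correlation.**

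| Assumed ρ | SD of differences, residual graft | Power for a 100% change (7.7 points) | Change needed for 80% power | Vital bone: power for 1 SD |
|---|---|---|---|---|
| 0 | 13.01 | 39% | 168% | 51% |
| 0.3 | 10.89 | 51% | 141% | 66% |
| 0.5 | 9.20 | 65% | 119% | 80% |
| 0.7 | 7.13 | 86% | 92% | 95% |

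For 80% power at 100%, the SD of the differences must be 7.7/0.996 = 7.73, so ρ = 1 − (7.73/9.2)²/2 = 0.647. At ρ = 0.65, vital bone would have about 92% power at 1 SD rather than the stated 80%. One common correlation therefore does not give both stated figures.

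**Step 7: number of pairs.** At ρ = 0.5, power for a 100% change is 79% with 13 pairs and 82% with 14.

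**Step 8: other variants.** At ρ = 0.5 a two-sided normal approximation gives 75.4% and a one-sided t-test 78.7%, both short of 80%. A one-sided normal approximation gives 84.2%, but the plan is two-sided.

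**Step 9: skew.** A normal curve with mean 7.7 and SD 9.2 puts 20% of values below zero, which a percentage cannot take. In simulations with an assumed gamma shape, paired-t power was about 67% for a doubling with unchanged SD (realised correlation about 0.45). It was just over 20% if the SD doubled as well, and about 87% for complete elimination of residual graft in one sinus.

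**The case against.** The strongest reply is that Section 7.1 already has the right form of words one sentence earlier, where 100% is a lower bound. On this view the closing sentence only summarises it and has lost a qualifier. That is a fair account of how the error arose. It does not cover the Study Summary, which has no qualifier, and a lower bound on the change needed does not support 80% power at the bound itself.

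A second reply is that the 1 SD rule is stated only for vital bone, and the two tissue measures need not share a correlation. This is true, and a correlation of about 0.65 or more for residual graft would make the claim correct. None is stated or justified, and lower values make the shortfall worse.

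A third reply is that the 65% is fragile because the inputs themselves point to skew. This stands. Power depends on the direction of the change and on whether the SD moves with the mean. Under the assumed gamma shape, complete elimination would exceed 80%. Section 7.2 also provides that "In the event that the distributions are skewed, and appropriate non-parametric test will be used", so paired-t power may not describe the analysis actually used. The 65% should be quoted only with its conditions. None of this supports an unqualified 80%.

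A 119% decrease is also impossible. At the quoted mean only an increase could be that large, and the corrected text should say so.

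**Conclusion.** The concern holds. On the protocol's own rule and inputs, the change in residual graft detectable with 80% power is about 119% of the quoted mean, not 100%. The 119% rests only on the implied correlation of 0.5 and the usual t-test assumptions. Power at 100% is about 65% on the same basis, and 39% to 86% over correlations of 0 to 0.7. It is approximate because residual graft is probably skewed.

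The error is confined to the closing sentence of Section 7.1 and the Study Summary. The vital-bone claims are not wrong; their only defect is the unstated correlation. The sample size of 10 is supported for vital bone. This should be fixed, because it concerns the stated power for a named primary outcome.

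**What to change.** Keep n = 10 and restate the closing sentence of Section 7.1 and the matching Study Summary text along these lines:

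> Ten pairs give 80% power (two-sided paired t-test, alpha 0.05) for a mean within-subject difference of 1.0 SD of the paired differences. Assuming a left-right correlation of 0.5, so that the SD of the differences equals the one-condition SD, and normality, this is about 50% of mean vital bone using the first cited study, about 24% using the second, and about 119% of mean residual graft. A decrease cannot exceed 100%, so a difference of 119% could only be an increase. Power for a 100% change in residual graft is about 65%.

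Add the range over assumed correlations of 0, 0.3, 0.5 and 0.7: power for a 100% change in residual graft of 39%, 51%, 65% and 86%, and a change needed for 80% power of 168%, 141%, 119% and 92%. Note that these figures are approximate, because the quoted SD exceeds the mean and Section 7.2 allows a non-parametric test if distributions are skewed. If the sponsor has grounds for a higher correlation for residual graft, it should be stated with its source.

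The 25-50% vital-bone range can stay, with 24% understood as the unrounded lower figure.

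The cost is wording in two places and a less favourable residual-graft figure. No subjects are added, and the endpoints, test and analysis set do not change.
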